# STUDY PROTOCOL

# **Social Behavioral Template**

#### 6.1.1 Data Collection

#### STUDY DESIGN OVERVIEW

The study is a single-group longitudinal study with periods of familiarization with devices, intervention using devices and mobile app, and maintenance follow-up (Figure 4). The primary aim is observing the intervention for feasibility, acceptability, and mathematical robustness. The secondary aim is observing psychological and biometric outcomes through assessments (Table 2) which are completed 1x/weekly during the entire study to test long-term effects (hypothesis 2-1-2 & 2-2-1) and 5x/daily during maintenance follow-up to test momentary effects (hypothesis 2-1-1 & 2-2-2). The secondary aim also includes an interview at the end of the study (hypothesis 2-3).

**Figure 4.** Individual participant timeline. Blue indicates measures for primary aims and red indicates measures for secondary aims.

Table 2. Surveys used for secondary aims. Appendix has instruments for dependent variable (#2a,2b), independent

variables fear of hypoglycemia (#3a, 3b), exercise self	-efficacy (#4), exercise self-regulation (#	
valence (#6), daily intention and competing demands  PHASE	Momentary	Weekly
	(Hypotheses 2-1-1, 2-2-2) (Timepoints T1-T2)	(Hypotheses 2-1-2, 2-2-1) (Timepoints T0-T2)
ASSESSMENT SCHEDULE	5x daily at random times within 3hr bins under ambulatory conditions of daily living	Weekly in controlled setting (tele-video in quiet room)
DEPENDENT VARIABLE††		
Cravings for Rest and Volitional Energy Expenditure (CRAVE) survey of motivation states for physical activity*	Score of 1-item want "right now" and 1-item aversion "right now"	Score of 5-item want "past week" and 5-item aversion "past week"
INDEPENDENT VARIABLES		
Fear of hypoglycemia†	Score of 1-item "next 3 hours" version	Weekly score of 18-item "past week" version
Fear of hyperglycemia ††	Score of 1-item "next 3 hours" version	Weekly score of 24-item "past week" version
Blood glucose metrics‡	Past 3 hours averages and slope	Weekly averages
Exercise self-efficacy 	N/A	Weekly score of 9-item "past week" version
Exercise self-regulation 	N/A	Weekly score 15-item "past week" version
COVARIATES		
Non-T1D-related affective valence states previously associated with CRAVE score (pleasure/displeasure  , activation/arousal  ).§	Score of 1-item "right now" versions	Weekly score of 1-item "past week" versions
Day of week, time of day	Timestamp	N/A
Weather (temperature, humidity, windchill for GPS location by National Weather Service)	Momentary value	Weekly averages

August 13, 2024

Version #7

Physical Activity Daily Intention  multiple choices (exercise in morning, occupational activity, etc  )	Daily state	Weekly frequencies
Competing Demands "How busy is today's schedule?"82	Daily state	Weekly averages
Illness "Were you sick yesterday?"	Daily state	Weekly frequency
Sleep (total, waketime after sleep onset)**	Daily state	Weekly averages

††Dependent variable for aim 2-1. For aim 2-2, this is an independent variable and the dependent variable is Actigraph-measured physical activity. \*Validated in ref for 5-item versions and ref for 1-item versions. †1-item is emerging new instrument and 18-item widely validated ( $\alpha$ =.89). ††1-item parallels fear of hypoglycemia item one row up, and 24-item is validated ( $\alpha$ =.92). ‡Assessed by Dexcom G6 continuous glucose monitor (mean error 9%-10%). Quantified as consensus metrics (Coefficient of variation, mean, time in target range [70-180 mg/dL], time above range, time below range i.e. hypoglycemic). §.41-.88 convergent validity. ||assess at wakeup and apply to all timepoints that day. \*\*Assessed by Actigraph GT9X. Each 60-s epoch will be scored as wake or sleep (Sadeh's algorithm).

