#### Mailing

After visit 1, participants will be mailed a package containing:

- a. Blood pressure monitor (Omron BP760N)
- b. CGM transmitter plus 6 sensors (Dexcom G6). If not already using. Issued by Dexcom under a research contract, not involving a prescription.
- c. Bluetooth ketone meter and test strips (Keto-Mojo GK+). The device also acts as a glucometer for CGM calibrations and sensor changes.
- d. Prepackaged snacks containing 15g fast-acting carbohydrates (e.g., Nestle Juicy Juice 125mL boxes, Glucose Tablets)
- e. Fitness smartwatch (Fitbit Inspire 3)
- f. Bluetooth Smart Insulin Pen (Companion Medical Inpen). If not a pump user. Issued by Medtronic under a research contract, not involving a prescription. A prescription for the participant's normal insulin in the correct cartridge for the InPen (3mL, U-100) will be obtained from the participant's primary diabetes care provider, or sent by a study physician through EPIC.
- g. Smartphone. If not already owned

August 13, 2024

Version #7

h. Actigraph GT9X Accelerometer. Programmed to run days 8-22, plus box to mail back so research team can download, reprogram for days 50-64, and mail to participant a second time.

In the event of lost items, up to 1 replacement will be provided, except items that are not essential for safety and have resale value (scale, fitness smartwatch, smartphone). Regardless of lost items, participants will be allowed to continue with other aspects of the study. For example, if they lose the smartwatch they can still use the exercise app with feedback missing the heart rate, steps, and sleep. Or if they lose the scale, they can still attend the weekly visits and complete the surveys and blood pressure readings. Participants will not be responsible for the cost of any lost or damaged items.

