#### Surveys

Participants will complete the first weekly "long-term" survey (Table 2, third column) on REDCap.

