The exported data include firstly exercise adherence, by tracking usage of exercise guidance (videos or guided outdoor walking). Fitbit heart rate readings verify exercise timing, duration, and intensity. The Borg Rating of Perceived Exertion prompt captures intensity for non-aerobic exercises such as weightlifting (Appendix 8c). The extracted data also include contextual variables that may predict vulnerability to missing exercise: 1) 24hr blood glucose derived from interstitial vales sampled every 5min by the CGM and expressed by consensus metrics (coefficient of variation, mean, % time >180, 70-180, <70mg/dL). 2) Fear of hypoglycemia the previous night and coming day (Appendix 8a). 3) Sleep Quality the previous night from self-report (Appendix 8a) and Fitbit (sleep time overestimation ~10%); 4) Competing demands and exercise plan (Appendix 8a); 5) Weather; (temperature, humidity, windchill) captured using GPS location and the National Weather Service API; 6) Day of the week (weekday vs. weekend). 7) Insulin dosing (including entered carbohydrates) from the participant's device (InPen, Tandem, Omnipod, or Medtronic). 8) Physical activity outside of exercise videos; captured by the proprietary Fitbit algorithm (intensity classification accuracy 85%, step counts ±3%;).

The above markers of individual context, day of the week, and between-participant characteristics, including demographics and clinical characteristics that can impede exercise (body composition, mobility limitations), will be exported from GlucoseZone to our Yale Secure Server for processing by our machine-learning code. The code is programmed to identify predictors of exercise "lapse," defined as the 3rd missed day of the week or 2nd consecutive missed day given that the goal is 150 min/week spread over ≥5 days. Thereafter, when the code detects these predictors, the research assistant running the code will signals the exercise coach to edit then send a specific encouragement message. E.g., if high blood glucose variability is a vulnerable state predictor, the just-in-time message meeting its occurrence would read: "Sometimes blood glucose can go up and down. You can still be active using the strategies you and your provider have discussed." This encouragement does not extend to suggestions of specific exercises or managing low blood glucose.

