#### 7.2.1 Secondary Objective Analyses (if applicable)

All statistical models for secondary objectives 1 and 2 will estimate intraclass correlation coefficient (ICC) to assess the proportion of variance explained by participant ID.

Secondary Objective 1 (STATISTICAL, MULTILEVEL MODELING). Examine whether recognized T1D-related physical activity barriers (fear of hypoglycemia, glycemic variation) predict momentary and long-term variation in motivation states for physical activity

**Hypothesis 2-1-1. Momentary predictors of motivation states.** We will develop two multilevel models for the dependent variables of want and aversion for physical activity (CRAVE 2-item "right now") respectively. The independent variables and covariates (Table 2) will be separated into momentary states for level 1, daily states for level 2, and demographics for level 3.

Hypothesis 2-1-2. Week-to-week changes in motivation states. We will develop two generalized linear mixed models for the dependent variables of want and aversion for physical activity (CRAVE 10-item "right now") respectively. A random intercept will incorporate correlations within-subject. We will include long-term assessed independent variables and covariates (Table 2, last column) along with a time categorical variable to estimate the contribution of changes coinciding with intervention (T0 to T1) and maintenance follow-up (T1 to T2).

Secondary Objective 2 (STATISTICAL, MULTILEVEL MODELING). Examine whether motivation states for physical activity predict momentary and long-term variation in physical activity behavior change, adherence, and maintenance resulting from a T1D motivational physical activity intervention.

August 13, 2024

Version #7

Hypothesis 2-2-1 – Predictors of physical activity behavior change and adherence over the intervention. We will develop a generalized linear mixed model for physical activity behavior testing WANT and SCT constructs as independent variables. A random intercept will incorporate correlation within-subject. We will include long-term assessed independent variables and covariates (Table 2, last column) along with a time categorical variable to estimate the contribution of changes from intervention (T0-T1) and maintenance follow-up (T1-T2).

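### The weekly sleep covariate required in the Hypothesis 2-1-2 model comes from a device not worn during the intervention, so it exists for at most 4 of 9 weekly surveys

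*Combined protocol and SAP*

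**What the plan says.** For Hypothesis 2-1-2, section 7.2.1 plans two mixed models, one for want and one for aversion, with a random intercept per participant. On the right-hand side it says: "We will include long-term assessed independent variables and covariates (Table 2, last column) along with a time categorical variable". The time variable is there to estimate "changes coinciding with intervention (T0 to T1) and maintenance follow-up (T1 to T2").

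The last column of Table 2 (section 6.1.1) lists sleep, as total sleep and wake time after sleep onset, in the form of weekly averages. The footnote to that row reads "Assessed by Actigraph GT9X. Each 60-s epoch will be scored as wake or sleep" and names no other source.

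Item h of the mailing list in section 6.1.1 gives the Actigraph schedule: "Programmed to run days 8-22, plus box to mail back so research team can download, reprogram for days 50-64". Table 1 shows the same two blocks, and the Visit 8 instructions have the participant put the device back on that day.

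The weekly surveys run from Visit 2 to Visit 10. Under Visit 2 (day 8) the text says "Participants will complete the first weekly" survey; the ninth is at Visit 10 (day 64). The study-issued devices are mailed after Visit 1 and set up at Visit 2, and the daily morning survey also starts at Visit 2.

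A second source of sleep data is collected but not assigned to this model. Under Tool #2, the lapse-prediction inputs include "Sleep Quality the previous night from self-report (Appendix 8a) and Fitbit". Table 1 shows the Fitbit in continuous use from Visit 2 to Visit 10.

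**The concern.** The covariate list and the device schedule do not fit together. The model is meant to describe how motivation states move across the intervention and the follow-up, with adjustment for weekly sleep. Yet the only named sleep instrument has been returned to the study team during the whole intervention. The gap is not caused by non-wear or dropout: it is built into the schedule and affects every participant in the same weeks.

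Missingness of this covariate therefore coincides with study phase, which is what the time variable encodes. If incomplete rows are dropped, the intervention weeks leave the model. If they are imputed, no Actigraph sleep from that phase is available to anchor the values. If the analyst drops sleep or substitutes another measure, that choice is made after the data are in, with nothing in the plan to guide it.

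The first weekly survey has a related problem. It asks about the week before day 8, when neither the study-issued devices nor the morning survey were running.

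**Working it through.** This is a count; no sample-size formula is involved, and the plan gives no number of complete weekly rows to reproduce.

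**Inputs**
- Weekly survey days 8, 15, 22, 29, 36, 43, 50, 57 and 64: Table 1 and the visit descriptions in section 6.1.1.
- Look-back of one week: Hypothesis 2-1-2 in section 3.2 and Table 2.
- Actigraph recording on days 8-22 and 50-64: mailing item h and Table 1.
- Fitbit, and the morning survey that supplies the diary covariates, on days 8-64: Table 1.
- Intervention from Visit 4 (day 22) to Visit 8 (day 50).
- Completers: section 7.1 expects 21. Check: 24 × 0.88 = 21.1.

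**Step 1. Nights covered in the week before each survey**

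| Survey day (visit) | Week described | Actigraph nights | Fitbit and diary days |
|---|---|---|---|
| 8 (Visit 2) | before device set-up | 0 | 0 |
| 15 (Visit 3) | familiarization | 7 | 7 |
| 22 (Visit 4) | familiarization | 7 | 7 |
| 29 (Visit 5) | intervention | 0 | 7 |
| 36 (Visit 6) | intervention | 0 | 7 |
| 43 (Visit 7) | intervention | 0 | 7 |
| 50 (Visit 8) | intervention | 0 | 7 |
| 57 (Visit 9) | follow-up | 7 | 7 |
| 64 (Visit 10) | follow-up | 7 | 7 |

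Requiring a minimum of 7, 4 or 1 nights gives the same set of usable surveys.

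**Step 2. Rows**
- Planned: 21 × 9 = 189.
- With Actigraph sleep: 21 × 4 = 84.
- Without: 189 − 84 = 105, and 105/189 = 56%. These are 21 × 4 = 84 rows from the intervention-week surveys and 21 × 1 = 21 from day 8.
- With Fitbit sleep instead: 21 × 8 = 168.

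**Step 3. Is 4 of 9 exact or a ceiling?** For fully complete rows it is a ceiling. Weekly weather is also in the last column and depends on GPS location. Table A1 (section 2.2) lists GPS only for GlucoseZone, which is downloaded at Visit 4 and shown in Table 1 only to Visit 8. Read literally, the day 15 and day 22 rows may lack weather, and the day 57 and day 64 rows may too.

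**Step 4. Visit windows.** Table 1 allows ±7 days. A Visit 5 held 3 days early would pick up 3 Actigraph nights. A late Visit 8 would pick up some only if the device were worn before that visit. The day 36 and day 43 surveys stay at zero for any permitted shift.

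**Step 5. Consequence for the time contrasts.** The documents give no day for T1. Section 3.2 describes T0-T1 as the four-week intervention and T1-T2 as the two weeks after it, which points to the day 50 survey. On that inference no row at T1 has Actigraph sleep, so a complete-row fit has nothing at T1 for either contrast. The familiarization-to-follow-up comparison would remain.

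**The case against.** The strongest reply is that the plan does not commit to a complete-row analysis. Section 7.7 says missingness will be screened and lists multiple imputation and Markov chain Monte Carlo estimation among the options. A reader might infer that the intervention phase will be deleted and the two contrasts lost outright. The documents do not support that: deletion follows only if incomplete rows are dropped, and losing both contrasts also needs T1 to be the day 50 survey.

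A reader might also infer that no sleep data exist for the intervention. That is wrong as well. Fitbit sleep and self-reported sleep quality are both collected in that phase, and the Fitbit overlaps with the Actigraph on days 8-22 and 50-64, so both could serve as auxiliary variables in an imputation. What is missing is Actigraph sleep.

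Nor does the first survey precede every device. Current CGM users and insulin-pump users bring their own, and may have glucose or insulin data for that week. Their day 8 rows still lack Actigraph sleep and the diary covariates.

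Finally, sleep is an adjustment covariate rather than one of the predictors named in Hypothesis 2-1-2, and section 7.1 says this hypothesis is not powered for significance but is meant to yield effect sizes. Both points are fair and limit the weight of the issue.

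The mismatch itself stands. Section 7.7 lists imputation as an option and says nothing about a covariate absent by design for all participants in one phase. An effect size for change over the intervention still needs usable rows from the intervention.

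**Conclusion.** The concern holds as an internal mismatch between the covariate list in section 7.2.1, the sleep source in Table 2 and the Actigraph schedule. On the nominal schedule, Actigraph sleep is available for at most 4 of 9 weekly surveys (at most 84 of 189 expected rows) and for none of the four intervention-week surveys.

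The row counts assume 21 completers, all nine surveys answered, visits on their nominal days and full wear. The loss of the T0-T1 and T1-T2 contrasts further assumes a complete-row fit and T1 at day 50; the first is not stated in the plan and the second is inferred from section 3.2. Under imputation the contrasts can be estimated, but the sleep adjustment in the intervention weeks would rest on other phases or on Fitbit and diary data.

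This should be corrected before analysis. It concerns one covariate of a secondary, unpowered hypothesis and does not touch the primary objectives. The point here is that covariate only; the Actigraph-measured activity outcome of Hypothesis 2-2-1 is a separate matter.

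**What to change.** - In Table 2, name Fitbit total sleep as the weekly sleep covariate for Hypothesis 2-1-2 in all phases, so that one instrument is used throughout. Include wake time after sleep onset only if the Fitbit export provides it; the documents mention Fitbit sleep time but not this component.
- Compare Fitbit with Actigraph sleep on the overlapping days 8-22 and 50-64, and report the agreement.
- Keep Actigraph sleep for the momentary models over T1-T2, where the device is worn.
- Fit the device-adjusted model from Visit 3 onward. Keep the Visit 2 survey in a companion model without device and diary covariates, so that the first baseline record is not lost.
- State the survey days that define T0, T1 and T2, and add a sentence to section 7.7 on covariates that are missing by design.
- Confirm that weekly weather can be obtained outside Visits 4-8. Also confirm that Fitbit nights from familiarization and follow-up are retrieved, since Table A1 routes Fitbit data through the GlucoseZone interface.

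With these changes sleep covers 8 of 9 surveys (168 of 189 rows), including all four intervention weeks, subject to those two confirmations.

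The cost is wording in Table 2 and sections 7.2.1 and 7.7, with no new data collection and no added participant burden. There are two downsides. The protocol puts Fitbit overestimation of sleep time at about 10%, and whether that is constant within a person is an assumption that the overlap check can only partly test. The Visit 2 record is also left out of the adjusted model.

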#### PROCEDURES FOR EACH VISIT ARE GIVEN BELOW:

#### VISIT 1 (Day 1)

On REDCap: consenting, medical history (verify from eligibility interview Appendix 1c), demographics form (Appendix 1d), contact information (Appendix 1e).

When possible, research staff will compare the collected medical and demographic information with EMR data accessed through EPIC (Yale patients) or Share Everywhere (non-Yale patients who have a MyChart account). In the event of any discrepancies, the staff will ask the participant for clarification to resolve the discrepancy.

#### **Monitor Symptoms**

The research assistant will ask the participant if they are having any of the symptoms overviewed on the consent form or any other injuries that could be made worse by exercising. In the event of positive responses, exercise physiologist (EP) [name] will contact them to ask follow-up questions, following protocols from the American College of Sports Medicine, to determine if they are indicative of pathology. If they are, [name] will report the episode to study physician [name] and the participant's own PCP and suspend the participant's exercise participation unless receiving PCP clearance to continue.

#### Mailing

After visit 1, participants will be mailed a package containing:

- a. Blood pressure monitor (Omron BP760N)
- b. CGM transmitter plus 6 sensors (Dexcom G6). If not already using. Issued by Dexcom under a research contract, not involving a prescription.
- c. Bluetooth ketone meter and test strips (Keto-Mojo GK+). The device also acts as a glucometer for CGM calibrations and sensor changes.
- d. Prepackaged snacks containing 15g fast-acting carbohydrates (e.g., Nestle Juicy Juice 125mL boxes, Glucose Tablets)
- e. Fitness smartwatch (Fitbit Inspire 3)
- f. Bluetooth Smart Insulin Pen (Companion Medical Inpen). If not a pump user. Issued by Medtronic under a research contract, not involving a prescription. A prescription for the participant's normal insulin in the correct cartridge for the InPen (3mL, U-100) will be obtained from the participant's primary diabetes care provider, or sent by a study physician through EPIC.
- g. Smartphone. If not already owned

August 13, 2024

Version #7

h. Actigraph GT9X Accelerometer. Programmed to run days 8-22, plus box to mail back so research team can download, reprogram for days 50-64, and mail to participant a second time.

In the event of lost items, up to 1 replacement will be provided, except items that are not essential for safety and have resale value (scale, fitness smartwatch, smartphone). Regardless of lost items, participants will be allowed to continue with other aspects of the study. For example, if they lose the smartwatch they can still use the exercise app with feedback missing the heart rate, steps, and sleep. Or if they lose the scale, they can still attend the weekly visits and complete the surveys and blood pressure readings. Participants will not be responsible for the cost of any lost or damaged items.

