### **SECONDARY**

Hypothesis 2-1-1: Fear of hypoglycemia and blood glucose trends over the past 3 hours will predict momentary motivation states for physical activity (timepoints T1-T2).

Hypothesis 2-1-2: Fear of hypoglycemia and glycemic metrics over the past week will predict motivation states for physical activity over the past week (timepoints T0-T2).

Hypothesis 2-2-1: Motivation states for physical activity over the past week will predict physical activity behavior change and adherence over the 4-week intervention period (T0-T1).

Hypothesis 2-2-2: Motivation states for physical activity over the past 3 hours will predict physical activity maintenance, over the 2 weeks following the intervention (T1-T2).

Protocol Number 2000035846

August 13, 2024 Version #7

Hypothesis 2-3: We expect interview themes among the proposed T1D population will include perception of connection among glycemic variation, fear of hypoglycemia, motivation states for physical activity, and performance of physical activity.

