# STUDY PROTOCOL Social Behavioral Template

# **6 Study Methods/Procedures**

6.1 Study Procedures

Table 1. Visit Schedule

	Pre-screening (Pre-consent)	Visit 1 Day 1	Visit 2 Day 8 ±7	Visit 3 Day 15 ±7	Visit 4 Day 22 ±7	Visits 5 Day 29 ±7	Visit 6 Day 36 ±7	Visit 7 Day 43 ±7	Visit 8 Day 50 ±7	Visit 9 Day 57 ±7	Visit 10 Day 64 ±7	Unscheduled Visit
Screening Phone Call	X											
Contact primary care provider for confirmation	X											
Informed Consent		X										
Demographics		X										
Clinical history		Χ										
Blood pressure			X	X	X	X	X	X	X	X	X	
Monitor symptoms		X	X	X	X	X	Х	X	X	X	X	
Devices			•				'				-	
InPen (if multiple daily injection user)			Continuou	ıs							>	
CGM			Continuo	ıs							>	
Fitbit			Continuo	ıs							>	
Morning survey monitoring daily living (Appendix 8a)			Continuou	ıs							>	
Actigraph GT9X (hip during day, wrist during night)			Continuou	IS	>				Continuous		>	
Intervention												
Mobile App					Continuou	s			>			
Outcome Evaluation											·	
Interview on App Features						X	X	X	X			
Exit Survey on App Features									X			

August 13, 2024 Version #7

Momentary Surveys on Motivation States									5x/day		>	
Weekly Survey on Motivation States			X	X	X	X	X	X	X	X	X	
Interview on Motivation States											X	
Adverse Events Reporting							-					
Adverse Events Reporting			X	X	X	X	X	X	X	X	X	X
Total Time (minutes)	15	30	45	35	65	65	65	65	85	35	80	15

\*The total time commitment for the study is the sum of these visits (575min) + mobile surveys (2min/survey \* 5 surveys/day \* 14 days = 140min) = 715 min, along with the target 150 minutes of exercise per week during the intervention and follow-up (150 min/week \* 6 weeks = 900min), for a total of 1625min or 27 hours.

[figure not shown]

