#### Put Actigraph GT9X (i.e., blinded hip and wrist watch) back on

Repeat visit 2 procedures.

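### The Actigraph is not worn during the intervention, so Hypothesis 2-2-1 has no adherence value from its named outcome, and the weekly sleep covariate in 2-1-2 is missing for all four intervention weeks

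*Combined protocol and SAP*

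**What the plan says.** Section 3.2 words Hypothesis 2-2-1 as: "Motivation states for physical activity over the past week will predict physical activity behavior change and adherence over the 4-week intervention period (T0-T1". Hypothesis 2-2-2 places the later interval after the app period: motivation states "will predict physical activity maintenance, over the 2 weeks following the intervention (T1-T2".

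The Table 2 footnote in section 6.1.1 fixes the outcome measure: "For aim 2-2, this is an independent variable and the dependent variable is Actigraph-measured physical activity". The same footnotes assign the sleep covariate (total sleep and wake time after sleep onset, as weekly averages in the last column) to the Actigraph.

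The Mailing list under Visit 1 sets the recording windows: "Programmed to run days 8-22, plus box to mail back so research team can download, reprogram for days 50-64". The Visit 8 procedures agree: "Put Actigraph GT9X (i.e., blinded hip and wrist watch) back on". So do the Table 1 arrows and section 7.6, which audits the device after each two-week period.

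In section 7.2.1 the 2-2-1 model takes the weekly predictors and covariates "along with a time categorical variable to estimate the contribution of changes from intervention (T0-T1) and maintenance follow-up (T1-T2"). The 2-1-2 model has a similar time term. The assessments behind both are "completed 1x/weekly during the entire study to test long-term effects (hypothesis 2-1-2 & 2-2-1").

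**The concern.** The hypothesis asks about adherence during a period in which its named measuring device is in the mail or waiting to be reprogrammed. Followed literally, the adherence half of 2-2-1 has no outcome data, and an analyst would have to pick a substitute after the data are in.

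The second effect is easier to miss. The motivation outcome in 2-1-2 is collected at every weekly visit, and its model is meant to estimate change that coincides with the intervention. One of its listed covariates is absent in exactly those weeks. The missingness is set by design and is complete within a phase, so it is not the scattered kind that section 7.7 appears to have in mind.

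**Working it through.** **Inputs.** Actigraph windows are days 8-22 and 50-64 (Mailing, item h). The intervention starts at Visit 4, day 22, and ends at Visit 8, day 50. Weekly surveys are at Visits 2-10, days 8, 15, ..., 64 (Table 1). The Fitbit is worn from day 8 to day 64 (Table 1). Expected completers are 21 (section 7.1; 24 × 0.88 = 21.1).

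**Reproducing the plan's own figure.** The compensation total shows how many Actigraph days the plan pays for:
- weekly visits: 5 + 8 + ... + 29 (nine visits) = 153
- CGM, Fitbit and daily survey: 3 × 56 days = 168
- Actigraph hip and wrist: 2 × 28 = 56
- momentary surveys: 200

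The sum is 153 + 168 + 56 + 200 = $577, exactly as stated. With 56 Actigraph days it would be 153 + 168 + 112 + 200 = $633. The two 14-day windows are therefore deliberate and not a slip in one sentence.

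**Coverage of the intervention.** Its length is 50 − 22 = 28 days. Overlap with days 8-22 is 0, and overlap with days 50-64 is 0. By calendar date only the visit days 22 and 50 touch both periods; none of days 23-49 is recorded.

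**Visit windows (±7 days).** If the programming stays fixed while visits move, incidental overlap is at most 7 of 28 days when the intervention shifts as a block. It is at most 14 of 42 days when Visit 4 falls on day 15 and Visit 8 on day 57. If wear follows the visits, as the Visit 8 text suggests, it is 0.

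**Device days in the seven days before each weekly survey.**

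| Survey day | 8 | 15 | 22 | 29 | 36 | 43 | 50 | 57 | 64 |
|---|---|---|---|---|---|---|---|---|---|
| Actigraph | 0 | 7 | 7 | 0 | 0 | 0 | 0 | 7 | 7 |
| Fitbit | 0 | 7 | 7 | 7 | 7 | 7 | 7 | 7 | 7 |

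Actigraph sleep is available for 4 of 9 surveys and for 0 of the 4 intervention-week surveys (days 29, 36, 43, 50).

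**Records for 2-1-2.** All surveys: 21 × 9 = 189. With Actigraph sleep: 21 × 4 = 84, none from the intervention. With Fitbit sleep: 21 × 8 = 168, of which 21 × 4 = 84 are from the intervention. These are upper limits, before non-wear or device loss.

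**What the Actigraph can still give for 2-2-1.** Days 8-22 are the level before the intervention, days 50-57 the level just after it, and days 57-64 a later maintenance level. Days 8-22 against 50-57, and 50-57 against 57-64, supply both time contrasts in section 7.2.1. The only blur is that the T1 value is taken in the first week after the app period.

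**The case against.** The strongest reply is that change does not require measurement inside the period. Accelerometer windows on either side of an intervention are an ordinary pre/post design, and coverage of 0 of 28 days is the wrong yardstick for it. This stands. A reader might infer from the schedule that the change question in 2-2-1 cannot be answered, but the documents do not support that. The blur at T1 should also be modest on the plan's own terms, because Table 1 counts participant time "along with the target 150 minutes of exercise per week during the intervention and follow-up".

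A reader might also infer that adherence data are lost. They are not. Under Visit 4, Tool #2, the plan tracks use of videos and guided walks and verifies it with Fitbit heart rate. What is missing is any text making that measure the 2-2-1 outcome, while Table 2 names a different one.

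On sleep, section 7.7 offers multiple imputation and Markov chain estimation, and nothing plans a complete-case analysis. So 84 of 189 is a bound and not the expected result. Imputation could draw on Fitbit sleep and the daily self-report of sleep quality. It would, however, have no observed Actigraph sleep in any intervention week, and would rest on assuming that the relation seen in other weeks carries over. For a weekly Actigraph activity outcome in 2-2-1, missing sleep costs nothing extra, because outcome and covariate are absent together.

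Finally, the exact placement of T0, T1 and T2 is inferred from section 3.2, since Figures 3 and 4 are not shown. If T0 means the whole baseline window, the pre/post reading fits even better, and the adherence and sleep gaps are unchanged.

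**Conclusion.** The point holds for adherence and for the sleep covariate. It does not hold as a claim that intervention change cannot be estimated. The named outcome for 2-2-1 covers 0 of 28 nominal intervention days, so adherence in that period has no value from it. The named sleep measure is absent for 4 of 4 intervention-week surveys in 2-1-2.

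The scope is narrow. Section 7.1 treats 2-2-1 as an effect-size estimate without a power target, and sleep is one covariate among several. The primary objectives are unaffected. So are 2-1-1 and 2-2-2, whose momentary data fall in days 50-64, when the Actigraph is worn. Severity is minor to should-fix.

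The conclusion assumes nominal visit days and the section 3.2 reading of T0-T1. The record counts assume 21 completers and full wear.

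**What to change.** 1. **Adherence.** In sections 3.2 and 7.2.1 and the Table 2 footnote, name the Tool #2 measure (video or guided-walk use, verified by Fitbit heart rate) as the 2-2-1 adherence outcome for the intervention weeks. Reserve the Actigraph for the change outcome.
2. **Change.** In section 7.2.1, define the Actigraph contrast as familiarization (days 8-22) against the first post-intervention week (days 50-57), with days 57-64 for maintenance. State the interval over which activity is summarized. Report as a limitation that the T1 value is taken just after the app period ends.
3. **Sleep.** Use Fitbit sleep as the weekly covariate in 2-1-2, and in any 2-2-1 adherence model that uses intervention weeks. This makes up to 168 of 189 records usable. Use Actigraph sleep in the four dual-wear weeks as an agreement check.

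**Cost.** Wording only, with no new data, visits or devices. The price is measurement quality. The protocol itself gives about 10% overestimation of sleep time for the Fitbit and no error figure for its wake time after sleep onset. None of the four dual-wear weeks is an intervention week, so agreement there may not carry over fully. A lost Fitbit is not replaced, which would lower the 168.
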